1.6.2 Specific Objectives

1. To understand the perspectives of stakeholders (school teachers, administrators, parents, community leaders and students) on a school-based FA training (YoFA) program among SSC.

Hypothesis 1: The perspectives of stakeholders like school administrators, teachers, parents, community leaders, and school children needs to be understood to design a comprehensive YoFA program

2. To assess school children's Knowledge, Attitudes (willingness to) and Practices (self-efficacy) (KAP) on trauma/injury FA via the built YoFA training to stop LTBs.

Hypothesis 2: School children have limited knowledge, self-efficacy and practices regarding trauma/injury FA

3. To evaluate the effectiveness and usability of the YoFA training program for SSC to respond to LTBs safely and promptly in their environs.

Hypothesis 3: The YoFA training Program is effective in improving the KAP of SSC and it is usable within the school and community setting.

4. To determine the barriers associated with implementing the YoFA program among early SSC in the Fako Division.

Hypothesis 4: There exist some barrier/challenges in implementing a YoFA training

program in secondary schools.

CHAPTER TWO

LITERATURE REVIEW

It is important to understand some aspects regarding first aid training for children in schools. Here, we will be highlighting the relevance of Advanced Trauma Life Support concepts, the injury burden among school children, the qualifications of potential educators, and the appropriateness of school-based training. There is a clear consensus on the necessity and benefits of teaching first aid in schools, as it equips children with essential life skills, enhances their confidence, and promotes a safer environment. Future research should focus on developing effective training programs tailored to this age group, considering the emotional aspects of learning and the varied contexts in which children may need to apply their skills particularly in our setting.

First aid training is an essential aspect of emergency preparedness, particularly for children aged 10 to 14 years. This age group is increasingly exposed to various risks, both in schools and everyday life. Here, we will explore four key areas related to first aid training for children: the concept of Advanced Trauma Life Support (ATLS), the injury burden among school children, potential educators of first aid, and the appropriateness of implementing first aid training in schools.

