- b) False

35. **When should a tourniquet be removed?**

- a) A tourniquet should never be removed unless instructed by a physician or EMS provider
- b) When the patient begins experiencing severe pain
- c) When a first responder arrives on scene
- d) When bleeding has stopped

36. **When packing a bleeding injury, it is important to push material as close to the bleeding vessel as possible.**

- a) True
- b) False

37. **After packing an injury to stop bleeding, it is not necessary to apply pressure any more.**

- a) True
- b) False

38. **How excited are you about learning this training?**

- a) Not excited at all
- b) A little excited
- c) Excited
- d) Very Excited

B) FGD and in-depth interview Guide for teachers, Parents and administrators

Welcome dear parents/ teachers

We just introduced a plan to implement a First Aid Training program designed to teach 10 to 14 years old (forms 1 to 3) stop life threatening bleeds to avert complications and to build a first aid culture in them as they grow up. In order to improve this program and understand whether this will be a beneficial program in this community, we are asking you, the parents and teachers of the students at this level, to participate in a focus group discussion about the proposed project.

We want to understand your thoughts and concerns and hear your reactions to the project and to one another. We will ask you to sign a permission slip allowing us to record and transcribe the discussion, however, there will be no way to link what was said to you and your opinions will have no effect on your you or child, their grades, or any other consequence. We will use the data to strengthen the program and to help us decide whether training students is a good way to improve care for bleeding. This research is being done in conjunction with the University of Buea and University of California Los Angeles as well as the National Institutes of Health. Are there any questions? If you have any questions or concerns, please contact [name] at **[name]** anytime during or after the study.

I am turning the tape recorder on [CLICK]

Does everybody agree to participate in this interview?

1. First, what are your general impressions of the YOFA program as described?
2. What do you see as the benefits for children this age?
3. What do you see as the shortcomings of this program for children this age?
4. What do you see as the benefits or shortcomings of YOFA on the broader community?

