How likely is it that a program using children this age will make the community safer / more prepared to face traumatic injuries?

Possible Barriers and Concerns

5. Are there any practical barriers or concerns to bringing the bringing YoFA training into schools among 10- to 14-year-olds? If yes, what are some of them? (That may be parental consent, curriculum integration, teacher training and student involvement).

6. How do you suggest these barriers/concerns might be overcome or improved?

Program design and delivery

7. What practical training parameters are important to you as a parent or teacher to make this training easy and safe to conduct? (Length, frequency & type of training)?
8. What role do you think parents and teachers should play in the implementation and ongoing support of the program?

Closing

Thank the participants for their valuable feedback and input.

Reiterate the importance of their perspectives in shaping the development of the "Stop the Bleed" young first aiders program.

Provide information on next steps and how the feedback will be used.

Interview Guide and FGD Guide for students

Opening of the interview with an ice-breaker question to put the students at ease, such as:"What are your thoughts on first aid training in schools?

1. What are your thoughts and feelings about starting a "stop the bleed" program for young first aiders in your school?
2. How do you think a program like this could help students your age, and what makes you feel that way?
3. What are some ways you think having classmates trained in basic bleeding control techniques could be helpful for everyone?
4. What worries or questions do you have about starting this program, and how do you think we could work together to solve them?
5. How do you imagine your friends would feel about the chance to become young first aiders, and what do you think might encourage or stop them from wanting to join?
6. In your view, what skills or information do you think are really important to include in the "stop the bleed" training for students like you?
7. What ideas do you have for making the program fun and interesting so that everyone wants to participate and learn?
8. How do you think having a "stop the bleed" program could change how your school thinks and acts about being prepared for emergencies?

C) ADAPTED SYSTEM USABILITY SCALE FOR THE YOFA TRAINING PROGRAM

Kindly indicate with the smileys below whether you think you will use the YoFA Skills learnt

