3.11 DATA ANALYSIS PLAN

A difference-in-difference analysis would be done to assess the change in KAPs before and after the intervention in. The posttest would be done immediately after the 4 days of training for each pool and 3 months after the training to assess the need for refresher course planning.

The exposure variables include training on LTBs from injury first aid and the use of these services by the trained students (e.g., the number of persons assisted or referred during the follow-up period of the training).

We will analyze survey data using R Software with a combination of descriptive statistics and parametric and non-parametric tests to establish statistically significant differences between pre- and post-test results and between the intervention and control groups.

Table 7: Objectives and their Indicators

Objective	Activities/process	Data collection tools	Data Source	Indicators
1. To understand the perspectives of stakeholders on YoFA training program among SSC	- In-depth interviews	-In-depth interview guides	School teachers, administrators, parents, community leaders and students	
2. To assess school children's KAP (willingness and self-efficacy on trauma/injury FA via the built YoFA training to stop LTBs.	- survey	-Questionnaire	- students	- Obtain baseline KAP Scores
3. To evaluate the effectiveness and usability of the YoFA training program for SSC to respond to LTBs safely and promptly in their environs.	-Training following a specific STB and LFRs program -Training students on specific modules of LTB FA - Pre and post test -Simulation exercises	- Use adapted tools from the SBEAT - Questionnaires - Evaluation form with questions how? What was the situation?where, and how?	Stakeholders, teachers, parents, students	- Change in knowledge scores -At least 50% of stakeholders rate the program as good/ expectations met - 70% of students rate the program as good/expectations met - Number of children who made use of the FA skills taught
4. To determine the barriers associated with implementing the YoFA program among early SSC in the Fako Division.	- Interviews - Survey	-Interview guides - Questionnaires	- Stakeholders, - Teachers, students	- Perceived reasons and challenges that hinder FA training in schools.

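### Question 5 of the adult interview guide names four barriers in the question itself, and the objective 4 indicator does not separate volunteered from prompted barriers

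*Protocol*

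**What the plan says.** Objective 4 in section 1.6.2 of the protocol is descriptive: "To determine the barriers associated with implementing the YoFA program among early SSC in the Fako Division". The hypothesis attached to it is an existence statement: "There exist some barrier/challenges in implementing a YoFA training" program in secondary schools.

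Table 7 (section 3.11) lists interviews and a survey as the activities for this objective. Its indicator is "Perceived reasons and challenges that hinder FA training in schools", with no count, proportion or split by how the answer arose.

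The adult guide in section 3.8, part B, serves both focus groups and in-depth interviews. Question 5 asks whether there are practical barriers or concerns and goes straight on: "If yes, what are some of them? (That may be parental consent, curriculum integration, teacher training and student involvement". Question 6 then asks how the barriers just discussed might be overcome.

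Earlier questions in the same guide carry no list. Question 3, for example, reads "What do you see as the shortcomings of this program for children this age". The student guide asks "What worries or questions do you have about starting this program, and how do you think we could work together to solve them" and names no barrier.

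**The concern.** An interview question that supplies example answers invites the respondent to agree with them. Here the examples sit inside the question, and no instruction tells the interviewer to wait for an open answer first. In a focus group, a list read aloud reaches every member at once. Because question 6 builds on question 5, the suggested solutions can inherit the same slant.

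Objective 4 is meant to show which barriers matter in Fako. Section 3.3 says that qualitative results will be used to adjust the training program, and Chapter Four promises solutions and a message to policymakers. If an echoed barrier and a volunteered one look the same in the results, the reader cannot tell how far the list reflects the community and how far it reflects the guide.

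**Working it through.** The protocol gives no figure for this point; its sample size calculation in section 3.5 covers only the quantitative part. The check is therefore a reading of the instrument, a count of how much of the planned data it touches, and a look at what Hypothesis 4 can show.

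**1. What the four examples are.** All four concern school-level arrangements. Section 2.2 also lists four barriers for sub-Saharan Africa: little research, restricted health spending, absent implementation plans, and doubts about cost-effectiveness. Money appears in that list but not among the examples in question 5. A respondent led by the bracket is therefore led towards some kinds of barrier and not others.

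**2. How much of the qualitative data uses this guide (Tables 2 and 3).**
- Adult interviews: 4 schools × (2 parents + 2 teachers + 1 administrator) = 20 of 28.
- Adult focus groups: 4 schools × (1 parent group + 1 teacher group) = 8 of 12.
- Sessions: 20 + 8 = 28 of 28 + 12 = 40, or 70%.
- Adults: 20 + 8 × 5 = 60 up to 20 + 8 × 8 = 84.
- All participants: 28 + 12 × 5 = 88 up to 28 + 12 × 8 = 124.

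These are planned counts. Section 3.9 lets interviews run to saturation, so the final numbers may differ.

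**3. What lies outside question 5.**
- Adult questions 1, 3 and 4 come first and are open.
- The student guide lists no barriers.
- Section 3.6 plans visits every two weeks during follow-up to record challenges, and evaluation forms at the end.
- Section 3.2 plans to identify challenges met in the three months before the summative evaluation.
- Table 7 adds questionnaires for objective 4.

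No passage ties the later sources to the four examples.

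**4. What Hypothesis 4 can show.** As worded, one barrier satisfies it. If it were read as met once any adult names a barrier, and each adult did so independently with probability p, the chance would be 1 − (1 − p)^n. The documents give no p; 0.05 and 0.10 are illustrative.

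| Units counted | n | p = 0.05 | p = 0.10 |
|---|---|---|---|
| Adults, groups of 5 | 60 | 0.954 | 0.998 |
| Adults, groups of 8 | 84 | 0.987 | above 0.999 |
| Adult sessions, each group one unit | 28 | 0.76 | 0.95 |

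The last row allows for answers within a focus group not being independent. These figures illustrate how little the hypothesis demands. They do not measure the prompting bias, for which the documents supply no input.

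**The case against.** The strongest defence is that adults can raise concerns freely before question 5 is reached. That question can be answered no, and its bracket may be a cue for the interviewer that is not meant to be read out. Other sources also feed objective 4, and separating spontaneous from prompted mentions is often left to a codebook. Most of this stands and limits the effect to part of the barrier list. It does not remove the point: the guide does not say that the bracket is a probe, and interviewers may differ in whether they read it.

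A reader might infer something stronger: that the plan has a rule confirming Hypothesis 4 as soon as one person names one barrier, and that this rule is almost certain to be met. The documents do not support that. No sentence states when the hypothesis is confirmed. Objective 4 is already descriptive, and no test or sample size depends on the hypothesis. The high probabilities describe an inferred rule, rest on assumed values of p, and fall when each focus group is counted as one unit.

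A reader might also take the student guide to be leading in the same way. Its question presumes some worry or question, but it suggests no answer.

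**Conclusion.** The point holds as a minor one about the instrument. Asked as written, adult question 5 can tilt answers towards four named barriers, and the objective 4 indicator does not show which barriers were volunteered. The guide concerned covers 28 of the 40 planned sessions, but only one question in it and the follow-on question 6 are affected. The size of any tilt cannot be derived from the documents, and it depends on whether interviewers read the bracket aloud. Hypothesis 4 carries almost no information, so reporting it as confirmed would add nothing. That is a matter of reporting and changes no analysis.

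**What to change.** - Ask question 5 without the bracketed list. Move the four items to interviewer probes, used only after the open answer is complete.
- When coding transcripts, mark each barrier as volunteered or prompted. Do the same for solutions given under question 6.
- For objective 4 in Table 7, report volunteered and prompted barriers separately by stakeholder type. Fixed denominators of 28 and 12 are not advisable, because the sample is purposive and interviews run to saturation.
- Report objective 4 as a description of barriers and do not present confirmation of Hypothesis 4 as a finding. The hypothesis itself need not be replaced, since nothing rests on it.

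The cost is one reworded question, one Table 7 entry, a short interviewer instruction and one extra code in the transcripts. No participants or sessions are added.

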2.1 CONCEPTUAL REVIEW

First aid, was earlier defined as the initial care provided for an acute illness or injury, with goals including: preserving life, alleviating suffering, preventing further illness or injury and promoting recovery. First aid can be initiated by anyone in any situation including self-care [21].

General characteristics of the provision of first aid, at any level of training, include: Recognising, assessing and prioritising the need for first aid; Providing care using appropriate competencies and recognising limitations; Seeking additional care when needed, such as activating the emergency medical services (EMS) system or other medical assistance.[1]

In some studies around the world, it was seen through qualitative and quantitative studies that, although people in varying fields are aware of the importance of first aid for their professional development (e.g. among teachers in Spain), there is no such training in their careers or schools. This raises a challenge in understanding how to act or react in case of emergencies on the job [22].

The ERC 2021 guidelines advise that yearly, Cardio-pulmonary Resuscitation (CPR) training should be provided to all schoolchildren. From 2015, the KIDS SAVE LIVES statement has recommended that all schools worldwide should offer two hours of instruction per year to students by the age of 12 [1]. Additionally, evidence shows that prehospital haemorrhage arrest using a tourniquet is more effective than waiting to reach a trauma centre before applying one. The latter has higher chances of transfusion within the first hour of arrival and higher odds of mortality from haemorrhagic shock

[23]. However, it must be the right type of tourniquet and it should be applied in the right way.

In some developed nations like Spain, the United States of America (USA), and Canada among others, the contents of FA are part of the official curriculum of primary education (i.e., aged 6–12 years) [24]. Studying the presence of FA in educational legislation in Spain showed that although it is included in primary school curricula and compulsory in secondary education, it is taught mainly during Physical Education classes only. It reveals the need to make it an individual course for optimum outcomes.

The Ecological model incorporates the individual, interpersonal, institutional, community, public policy and chronosystem in the uptake and implementation of the YOFA program.

[figure not shown]

Figure 1: Illustration of Bronfenbrenner's ecological framework by Mash in 2019

The PPPM guides us through the planning process to avoid missing aspects important to a project by first knowing the outcomes, and then walking back to address some factors that will enable us to reach our expected results.

Predisposing,

Reinforcing and

Enabling Constructs in

Educational

Diagnosis and

Evaluation; aim to map educational 'diagnoses and planning' [48].

Policy,

[figure not shown]
Regulatory, and

Organisational Constructs in

Educational/Ecological and

Environmental

Development (guides socio-ecological assessment and planning) [48,49].

We will be using these two as the components of the former are incorporated in the later.

Predisposing Factors to performing skills from the YoFA program taught:

Knowledge (Training given), attitudes, and practices, motivation, self-efficacy.

Enabling factors: Antecedents of behaviour that facilitate motivation to perform the behaviour e.g., accessibility to FA “Stop the bleed” kit, to a telephones availability of a teacher to guide them through, and Health facility to receive the patient, skills, and laws.

Reinforcing factors: Rewards or punishments following or anticipated as a consequence of behaviour e.g., does the family encourage the child to learn the FA skills and apply what is learnt? What is/are the thoughts of peers, teachers, and other stakeholders? (here we see the interpersonal and community aspects of the ecological model come into place).

2.2 CONTEXTUAL REVIEW

Approximately 5.1 million deaths each year in sub-Saharan Africa (SSA) can be linked to conditions that might have been addressed through prehospital and emergency care [25], but which is however below standard or under-developed in SSA. Thus, the World Bank has been promoting first-aid training as. A cost-effective way to lower the injury and disease burden with an averted Disability-adjusted life year (DALY) of only 8 USD [25]. While the majority of research showcasing the effectiveness of adult first aid training programs has been carried out in Western settings [26–29], some studies from sub-Saharan Africa and various African Red Cross-National Societies conduct first aid training for adult laypeople. However, these trainings mostly took into consideration the Western context. There was an increased need for first aid in the SSA context by the African Red Cross societies, which gave birth to the AFAM (Africa First Aid Materials) in 2011 [30,31].

Given the growing evidence from Western nations indicating that children and

adolescents between the ages of 5 and 18 can acquire specific first aid skills and are open to offering assistance [32–34], instructing children in first aid appears to be a favorable approach for maximizing its effectiveness. Before Buck et al., in 2020, there was no study to test first aid training effectiveness among children in the African context and this led to the development of an educational pathway for FA training among kids [14].

In SSA, there were some barriers to FA training identified which include: (1) Limited scientific research and publication on the topic in SSA has contributed to a limited understanding of the specific barriers to FA training there [35] and in the SWR. (2) The limited resources allocated to healthcare spending. This restricted healthcare spending may impact the availability and accessibility of first-aid training programs, thereby acting as a barrier to widespread implementation [14]. (3) The lack of implementation plans for FA training in most SSA countries may contribute to the prevalence of barriers. The absence of comprehensive strategies and initiatives to promote and implement FA training programs could hinder their effectiveness and reach [35]. (4) The cost-effectiveness of a comprehensive FA training implementation program in LMICs including Cameroon is a current and foreseen problem [14].

2.2.1 Importance of First Aid Skills among School Children and Teachers

Given the challenges in accessing timely medical care, it becomes crucial for school children and teachers to have basic first-aid skills. The immediate care given to any person in a medical emergency, as provided by first aid, can significantly save lives [36,37].

The lack of formal first aid training in the teaching curriculum of most medical schools further emphasizes the need for first aid skills among school children and teachers. This is supported by the American Red Cross, which offers first aid programs for schools,

allowing teachers and administrators to train their students in first aid for free [18,19].

In addition, a study aimed to analyze the opinions and knowledge of future teachers at a Spanish public university regarding training and the need for first aid. The findings of this study can further support the importance of integrating first aid training into the education system [22].

The combination of inadequate access to health care facilities and emergency services in certain regions and the potential for first aid skills to make life-saving differences underscores the importance of promoting FA skills among school children and teachers.

2.2.2 Potential Impacts of First Aid Training on Reducing Injury-Related Morbidity and Mortality in the School Setting and Beyond

First aid training in the school setting can have a significant impact on reducing injury-related morbidity and mortality. Here are some potential impacts supported by some studies:

Immediate Assistance and Survival Rates: In rural Bangladesh, it was seen that effective bystander cardiopulmonary resuscitation (CPR) provided immediately after cardiac arrest can double a person's chance of survival by maintaining vital blood flow to the heart and brain [38].

Studies conducted in developed countries on non-fatal injuries have reported first aid to play a significant role in reducing mortality rates [38].

First aid offered by an untrained or trained provider is increasingly essential to reduce mortality and severity of injuries in developing countries [38–41].

Reduction in Severity of Injuries:

Research on severe non-fatal injuries such as burns, blunt trauma, and road traffic

incidents in high-income settings has found a significant reduction in mortality rates when first aid was applied [38].

Disaster Preparedness: Community first aid training for disaster preparedness can play a critical role in saving lives and reducing morbidity at the scene in the immediate aftermath of a disaster [42].

Educational Impact:

Providing necessary education with more effective methods, such as role-playing, can be effective in reducing mortality and morbidity due to lack of first aid care in crucial moments [43].

First aid training programs should be introduced at the school and college level in developing countries to decrease the early mortality and morbidity of accidents and emergencies [44].

Impact on Children's Safety: Accidents in schools are a significant cause of childhood injuries and deaths, and all staff needs to have first aid training to ensure the safety of children [45].

With all this, it means first aid training in the school setting has the potential to significantly reduce injury-related morbidity and mortality by providing immediate assistance, reducing the severity of injuries, and preparing individuals to respond effectively in emergencies. First aid and home safety training – with a focus on

